# **VERSION NUMBER/DATE:**

Version 12 (4/22/19) Water park pass for wearing the actigraph enough.

### **VERSION HISTORY:**

V EI (OIOIV I			
Revision	Version	Summary of Changes	Consent
#	Date		Change?
1	9/21/2015	Original application submitted to IRB	
2	10/25/2015	Response to stipulations	Υ
3	10/12/2016	Added a consent form for Action Team	Υ
		members	
4	3/27/2017	Final recruitment materials	N
5	4/26/2017	Final consent and assent forms and phone	Υ
		screener	
6	6/6/2017	Revisions to parent survey	N
7	2/8/2018	validation for migration to ETHOS	N
8	3/28/18	Cohort 2 recruitment materials	N
9	9/7/18	Recruitment trinkets and in person screening	N
10	9/13/18	Current participants send flyers to friends	N
11	2/5/19	Measurement at school and gift cards for interim	N
		child height and weight	
12	4/22/19	Water park pass	N

**Study Summary** 

Study Title	New Ulm at HOME (NU-HOME)						
Study Design	Randomized Controlled Trail						
Primary Objectives	Primary aim: To test the effectiveness of the NU-HOME program, a family-based health promotion intervention to prevent excess weight gain among 7-10 year old children. The main hypothesis is that children in the intervention group will have significantly lower body mass index z-scores (BMIz), relative to children in the control group at post-intervention (7 months), after adjustment for baseline values.						
Secondary Objectives	Secondary aims: To examine intervention effects on the following family- and child-level outcomes:  1) Home availability of healthful foods and beverages and quality of those served at family meals and snacks.  2) Children's dietary intake (e.g., calories, fruits and vegetables, sugar-sweetened beverages).  3) Children's minutes of moderate-to-vigorous physical activity and sedentary behavior per week, particularly screen time.						

VERSION DATE: 4/22/19

Primary Study Intervention or Interaction	The 7-month NU-HOME program is based on Social Cognitive Theory and a socio-ecological framework to prevent childhood obesity by addressing home environments and family and individual health behaviors through promotion of healthful family meals, snacks and beverage consumption, and the promotion of physical activity through collaboration with community partners.							
Study Population	Action Team = Community leaders who were defined by NIH as research participants as part of Community Based Participatory Research (CBPR) Main Trial = Children ages 7-10 and the parent/guardian in their family who prepares most of the meals							
Sample Size	Action Team = 14-20 Main Trial = 120 Parent child dyads or 240 people total							
Study Duration for Individual Participants	Action Team members = 5 years Main Trial participants = 1.5 years							

## 1.0 Objectives

## 1.1 Purpose

Primary aim: To test the effectiveness of the NU-HOME program, a family-based health promotion intervention to prevent excess weight gain among 7-10 year old children. The main hypothesis is that children in the intervention group will have significantly lower body mass index z-scores (BMIz), relative to children in the control group at post-intervention (7 months), after adjustment for baseline values.

Secondary aims: To examine intervention effects on the following family- and child-level outcomes:

- 1) Home availability of healthful foods and beverages and quality of those served at family meals and snacks.
- 2) Children's dietary intake (e.g., calories, fruits and vegetables, sugar-sweetened beverages).
- 3) Children's minutes of moderate-to-vigorous physical activity and sedentary behavior per week, particularly screen time.

#### 2.0 Background

## 2.1 Significance of Research Question/Purpose

New Ulm at HOME (NU-HOME) is a unique research collaboration between leaders in a rural community and academic obesity researchers. The proposed partnerships include the University of Minnesota (UMN), New Ulm local health care system (Allina Health), Minneapolis Heart Institute Foundation (MHIF), Brown County Public Health, local elementary schools, UMN extension service, local colleges and several existing community stakeholder groups. Our long-term goal is to establish a sustainable, effective intervention to prevent excess weight gain in children in rural communities. The objective of the proposed research is to test the effectiveness of the NU-HOME program, a family meals-focused health promotion intervention to prevent excess weight gain among 7-10 year old children (n=120) in the New Ulm rural community.

#### 2.2 Preliminary Data

VERSION DATE: 4/22/19

Our research team has completed extensive preliminary studies to support the proposed research, including a pilot randomized controlled trial (RCT) (NIH R21-DK0072997), a full-scale urban RCT (NIH R01-DK084000), a survey of rural parents and several adult-focused rural health promotion programs (HONU).

Healthy Home Offerings via the Mealtime Environment (HOME) pilot. The HOME pilot study consisted of formative research ([name] et al., 2011) and a two-arm RCT to prevent childhood obesity ([name] et al., 2010). We successfully met feasibility and acceptability aims for recruitment (n=44), retention (100%) and implementation (5sessions). The intervention included interactive family nutrition education activities, child cooking skills development, taste-testing, parent groups (meal planning and preparation support), and hands-on meal preparation with the entire family. Satisfaction and attendance were high; 86% of families attended at least four of five sessions. Significant intervention effects were found at post-intervention for increased child food preparation skills (M=17.5 vs. 15.2, p<.01) and parental report of children helping to make dinner (M=1.9 vs. 1.6, p<.01). Intervention versus control homes showed trends of higher fruit and vegetable availability (M=23.7 vs. 21.7, p=.12) and lower availability of quick, high-fat microwaveable foods (M=2.3 vs. 3.0, p=.11). Trends of higher intakes of fruits and vegetables (M=3.5 vs. 2.6 servings, p=.08) and lower intakes of sweetened beverages (M=0.4 vs. 0.7 servings, p=.09) among intervention compared to control children were also apparent. As expected in this pilot study, we did not see significant BMI change differences by treatment group at post-intervention.

**HOME Plus full-scale trial.** The recently completed full-scale HOME Plus study RCT (intervention and attention-only control) with 160 families (8-12 year-old child and parent/guardian) was conducted in urban communities using a staggered cohort design (two cohorts) ([name] et al., 2014). Eligibility included child BMI>50th percentile; English literacy; no plans to move within 6 months; and no severe medical conditions prohibiting study participation. Recruitment and baseline assessments occurred in summers of 2011 (Cohort 1) and 2012 (Cohort 2), followed by randomization (n=81 intervention families, n=79 control families). Participants were representative of the larger county; 71% white (child), 44% overweight/obese (child), 35% household received economic assistance, with full representation of the economic range; however, HOME Plus parents were more likely to have a college degree (61%). Data collection was very successful with 100% compliance at baseline, 93% retention at post-intervention and 89% at follow-up (21-months post randomization). Each assessment included psychosocial surveys and anthropometry (parent and child), puberty assessment (child), three 24-hour dietary recalls (child), home food inventory (parent), and a family meal inventory of 7 dinners (parent). Families randomized to the intervention attended 10 monthly sessions delivered by trained interventionists to multiple family groups (approximately 5-10 families) in community settings. Other family members also attended sessions or childcare (75% of families brought additional family members). The intervention focused on experiential activities and included parent discussion groups, hands-on nutrition activities, taste-testing, and family meal preparation. Participation was high with 68% of families attending at least 7 of 10 inperson sessions and 84% completing at least 4 of 5 goal-setting calls which used motivational interviewing techniques. Families randomized to the control group received monthly newsletters with healthful eating tips. The intervention had a promising reduction in excess weight gain when treatment groups were compared for the entire sample. Moreover, given the influence of puberty on weight gain, post-hoc stratification analyses were conducted to assess effects on BMI-z-scores by pubertal onset; findings indicated a statistically significant pubertal onset-by-treatment group interaction at both post-

VERSION DATE: 4/22/19

intervention (p=0.01) and follow-up (p=0.02). Sub-group analyses indicated a main effect of treatment among prepubescent children only, at both post-intervention (p=0.03) and follow-up (p=0.001). These findings suggest family meals-focused programming may be efficacious to prevent children's excess weight gain prior to pubertal onset. Thus, the proposed study is justified in using BMI-z-score as the primary outcome and recruiting 7-10 year old children.

Surveys of parents living in rural communities. Since the previous grant submission, we conducted a survey at the Minnesota State Fair in August 2014 to gather information from rural parents (n=174) about their family meal behaviors and interest in attending a program. such as the one proposed. Parents were eligible if 1) s/he was the family's primary meal preparer; 2) had a child between the ages of 8-12 who lived with them at least 50% of the time; and 3) had a rural zip code. Rural was defined using ZIP Rural-Urban Commuting Area Codes (RUCA) (unpublished data). Using RUCA codes allowed rural participants to be divided into groups from isolated, small rural, and large rural communities. Results indicated 80% of rural families eat family meals 4 or more days per week, comparable to the national (78.4%) rate (http://mchb.hrsa.gov/nsch/2011-12/health/index.html). Nearly three quarters of participants (73%) said they would be interested in attending in-person community-based family sessions focused on cooking and healthy eating. Of those interested, the majority (70%) was also interested in an online component; most parents (91%) reported ready access to the internet. Families reported driving long distances for everyday routine activities (e.g., traveling an average of 11-15 miles to work, for healthcare or to purchase groceries) and were willing to travel an average of 16 miles to attend a family meals-focused program.

Existing New Ulm health promotion programs. The HONU Project, launched in 2009, is a 10-year community demonstration project aimed at reducing adult myocardial infarctions and modifiable heart disease risk factors in the rural community of New Ulm (Boucher 2008) (VanWormer et al., 2012). New Ulm is located about 100 miles southwest of the Twin Cities metropolitan area in an agricultural region of the state. Healthcare is provided primarily by one system (Allina Health) that operates in New Ulm as New Ulm Medical Center (NUMC), the only clinic and hospital (35 beds) located in the community. The HONU Project is a collaborative partnership of Allina, the Minneapolis Heart Institute Foundation (MHIF), NUMC and the community. The MHIF leads design and implementation of the project through partnership with NUMC and the community. The project has primarily been funded through grants to MHIF from Allina, CDC, USDA and foundations. The community is represented by a 12-member steering committee that includes representation from NUMC, New Ulm city officials, Chamber of Commerce, school district and local colleges, Brown County Public Health, community organizations and the general public (including parents). The committee provides input on strategies to ensure interventions are tailored to New Ulm community audiences and helps promote community engagement. Research and evaluation work is coordinated by staff at the Division of Applied Research at Allina. For evaluation purposes, the target population of HONU interventions is adults ages 40-79 residing in the 56073 zip code (13,290 adults; includes New Ulm). Baseline assessments (2009) of dietary intake and obesity showed only 17% of New Ulm adults ate 5+ servings/day of fruits and vegetables, well below guidelines, and 35% of adults were overweight and 41% were obese (Van Wormer et al., 2012). These health indicators along with lower median household income indicate these adults are at risk for continued poor health. Building on lessons learned, HONU approaches improving population health through adult- focused interventions integrated into healthcare, worksites, and the larger community by modifying the environment. A recent evaluation found

VERSION DATE: 4/22/19

participation in any two component HONU Project programs was associated with significantly higher odds of blood pressure control two years later among those with uncontrolled blood pressure at baseline (Sillah et al., 2014). With national trends for hypertension remaining stable for the last decade, this decrease is exciting. In 2011-2012, approximately 500 residents registered for a holiday weight management program. Seventy percent of those retained (280-300), either maintained (18%) or lost (52%) weight, with mean weight loss of 4.2 lbs. Thus, HONU interventions appear to be making a difference in the health of adults in the community but there is a need, and a community desire, for family-focused programs. To date, HONU nutrition interventions have primarily focused on environmental reengineering to increase availability of healthful options in restaurants, grocery stores and convenience stores (Pereira et al., 2014); community-wide health marketing campaigns; adult nutrition education and weight management; and school-based initiatives to improve food at concessions.

# 2.3 Existing Literature

Childhood obesity is a serious public health problem (Ogden et al., 2014; NIH, 2011). Although previous environmental approaches to obesity prevention show some promise, few studies significantly engage parents or focus on the home environment, which is essential to promote healthful behaviors at home. Parents are primary role models for healthful eating (Draxten et al., 2014) and activity (Trost et al., 2011) and gatekeepers for food and beverage availability and degree of inactivity at home. Moreover, for children, the home setting is where most calories and energy dense foods are consumed (Briefel et al., 2009) and where most sedentary behavior occurs, particularly screen time (Rideout et al., 2010) (e.g., television). Children in rural communities are particularly vulnerable regarding increased risk for obesity and diabetes (USDHHS, 2011; Singh et al., 2010; Lutfiyya et al., 2007; Rockeymoore et al., 2014; NAC on Rural Health, 2011); owing in part to poverty (Lutifiyya et al., 2007) and lower access to healthful foods and physical activity opportunities (Yousefian et al., 2011; Seguin et al., 2014). Thus, effective programs that engage families in rural communities to prevent excess weight gain among children are critically needed.

### 3.0 Study Endpoints/Events/Outcomes

#### 3.1 Primary Endpoints/Events/Outcomes

Primary aim: To test the effectiveness of the NU-HOME program, a family-based health promotion intervention to prevent excess weight gain among 7-10 year old children. The main hypothesis is that children in the intervention group will have significantly lower body mass index z-scores (BMIz), relative to children in the control group at post-intervention (7 months), after adjustment for baseline values.

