Participants will complete measurements at three time points: baseline (before randomization), at post intervention (8-10 months after randomization) and at follow-up (14-16 months post randomization). At baseline, adult participants will provide written consent for participation and children will provide written assent. Data collection will be conducted in a quasi-group format (individual families working with individual staff) in convenient community locations, simultaneously. Based on our previous work, baseline assessments should take 1.5-2 hours, with shorter subsequent assessments. Trained study-staff will measure the height and weight of the adult and child participants. Online surveys will be completed on an electronic device (laptop, ipad, phone) by the adult participant to assess household level data (e.g., home food availability, family meal frequency and environment, nutritional quality of foods served at meals and snacks) and individual-level data (physical activity, usual fruit and vegetables intake). The parent and child will also participate in two interviews about the food the child ate in the past 24-hours. (Change in protocol from child interview to parent and child interview and from three to two interviews was approved 4/24/17.) The child will also wear an accelerometer to assess their physical activity. The child participant will also complete surveys to assess individual level data (e.g., fruit and vegetable preferences). Children will also complete two additional midpoint measurements.

During the two additional short data collection visits, child participant's height and weight will be measured and they will answer questions about physical activity, particularly at school, and healthy eating. (Change in protocol for additional child measurement was approved 4/24/17.) Children will be measured after school, removed briefly from class during school or measured at their home. Principals have provided support for measuring students at school and parents will be notified in advance of the measurements by text, email, or letter (depending on their preferred method of communication).

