Following baseline data collection, families will be randomized to the intervention program (NU-HOME; n=60 families) or a delayed intervention (n=60 families) in a staggered cohort design (two cohorts). The 7-month NU-HOME program aims to prevent childhood obesity by actively engaging children and parents/guardians to prepare regular, nutritionally-sound and appropriately-portioned snacks and meals eaten together and by reducing sedentary behavior, particularly screen time. The NU-HOME intervention program will promote physical activity through the existing programs of our community partners and resources in the community as well as through the study website. The 7-month intervention will be delivered to multiple family groups in convenient community settings. Intervention families will participate in seven monthly, two-hour sessions. All household members will be invited to participate in the sessions, as the inclusion of the entire family will facilitate comprehensive support for increasing the healthfulness of the home environment. Sessions will include an introduction and food preparation with all family members, separate adult and child sessions, and end with concluding statements, home activity assignments and enjoyment of a large group "family meal." The Research Team will develop a website for intervention participants. (Change in protocol to provide UMN accounts for intervention participants on secure UMN website developed specifically for the NU-HOME study was approved 10/2/17.) Intervention families will be allowed access with a secure, password

VERSION DATE: 4/22/19

protected login. They will have access to sessions that will be augmented online and will cover session content, video demonstrations and session materials (e.g., recipes) for both parents and children. The Research Team will coordinate with Heart of New Ulm (HONU) webmasters to link the NU-HOME website to the HONU main webpage after the research is complete. Intervention staff will establish and maintain rapport with families in sessions and will support families by phone four times during the intervention. Calls will use established protocols to employ motivational interviewing techniques such as reflective listening, agenda setting, and eliciting change talk to set goals and support behavior change and self-monitoring. All data collected as part of these calls will be entered in a secure REDCap database.

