### 5.3 Follow-Up

Data will be collected at post intervention (8-10 months post randomization) and at Followup (14-16 months post randomization)

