# 19.0 Provisions to Monitor the Data to Ensure the Safety of Participants 19.1 Date Safety Monitoring

The intervention and measurement protocols pose minimal risk to participants. Because of this low risk status, the Data Safety Monitoring Plan (DSMP) for this trial focuses on close monitoring by the principal investigator (PI) in conjunction with a safety officer ([name], a Professor with the School of Nursing at the University of Minnesota, Director of the Center for Adolescent Nursing, and Director of the Healthy Youth Development-Prevention Research Center). Safety reports will be sent to the PI, and the safety officer. The Evaluation Director will be responsible for assembling the data and producing these reports, as well as assuring that all parties obtain copies of these reports. We plan to collect injury data from the treatment and control (wait-list) group monthly during the 7-month intervention. We do not expect many injuries as a result of participating in the proposed intervention program. However, there is a possibility of injuries (e.g., minor burns, cuts) during the cooking component of the intervention. It is anticipated that most injuries related to cooking activities in a healthy child/parent population would be mild in nature and allow a complete return to the same activities after a brief recovery period. If necessary, alternative meal preparation activities (e.g., mixing, washing) will be substituted during the brief

VERSION DATE: 4/22/19

recovery period. An Adverse Event Form will be used by the study staff to report injuries or other adverse events that occur as a result of the intervention, particularly the cooking component. The safety officer will review, collate, and evaluate adverse events in real-time. Any serious adverse events reported to the University of Minnesota IRB will also be reported to the NIH funding institute. All adverse events will be evaluated by the Safety Officer and the principal investigator within 72 hours and reported to the UMN IRB; serious adverse events within 24 hours. Any study-related serious adverse event will be reported to the NIH funding institute within 2 weeks; all others will be included in the annual report to NIH funding institute. The frequency of data review for this study differs according to the type of data and can be summarized in the following table:

Data type	Frequency of review						

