Subject accrual rate (adherence to protocol regarding demographics, inclusion/exclusion) and retention rate	
 
Bi-monthly during the trial recruitment period for cohorts 1 and 2
 
At the completion of each of the three measurement periods for cohorts 1 and 2
 
						
Adverse event rates (injuries)	• 24-72 hours						
Compliance with intervention program	At completion of sessions 3, 6, and 10 of the intervention program						
Safety report	Every 6 months						

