#### 25.0 Resources Available

The study is not being conducted by a student researcher.

We feel we have the ability to recruit the target number of participants and have plans in place to expand our target area if necessary. Our team's evaluation of MN Department of Education data of the New Ulm 56073 zip code indicates there are approximately 725 7-10 year old children. Thus, we would need to recruit about 16% of children in New Ulm to meet our goal of 120. Although we do not anticipate difficulty with recruitment given the high participation rate of adults in HONU programs (70% of targeted adults), if it appears that recruitment will be difficult, we will also recruit from the neighboring community of Springfield with whom our community partners have an established relationship. Extending our reach beyond New Ulm to include Springfield will increase our pool of eligible children.

As outlined below, the study is funded for 5 years with time allocated to adapting the program (year 1), recruiting participants (year 2 for cohort 1 and 3 for cohort 2), competing baseline, post intervention (8-10 months after randomization) and follow-up (14-16 months after randomization) data collection (years 2-4), delivering the seven month intervention program (year 2 for cohort 1 and year 3 for cohort 4), delivering the delayed intervention, and dissemination the findings.

Study Timeline																
	Year 1		Year 2			Year 3			Year 4			Year 5				
Steering Committee Meetings																
Stage 1 (CBPR adapt program)																
Stage 2 (RCT) Hire and train																
Cohort 1																
Cohort 2																
Stage 3 (Delayed intervention)																
Stage 4 (Dissemination)																

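### Does the 7-month label on the primary endpoint conflict with a visit set 8-10 months after randomization, and does a compliance review at session 10 of seven matter?

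*Combined protocol and SAP*

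**What the plan says.** **Endpoint label.** The Study Summary, section 1.1 and section 3.1 state the main hypothesis in the same terms: lower BMI z-scores "relative to children in the control group at post-intervention (7 months), after adjustment for baseline values". None of them gives a starting point for the seven months.

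**Visit schedule.** Section 4.1 has families measured at baseline, "at post intervention (8-10 months after randomization) and at follow-up (14-16 months post randomization"). Section 5.3 repeats it: "Data will be collected at post intervention (8-10 months post randomization"). Section 5.2 gives the same window, and section 25.0 lists "post intervention (8-10 months after randomization) and follow-up (14-16 months after randomization) data collection (years 2-4").

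**Programme length.** The Study Summary says "The 7-month NU-HOME program is based on Social Cognitive Theory". Section 4.1 says "Intervention families will participate in seven monthly, two-hour sessions". Section 19.1 plans injury data collection "monthly during the 7-month intervention".

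**Analysis.** Section 17.1 compares the arms on change from baseline to post-intervention, which it describes as the immediate effect. It treats the follow-up visit separately, as the test of a sustained effect. It names no month.

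**Compliance review.** The table in section 19.1 sets this "At completion of sessions 3, 6, and 10 of the intervention program".

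**The concern.** The time point is part of what defines a primary endpoint, and section 3.1 is where a reader looks for it. Seven months from randomization lies outside the 8-10 month window, so on that reading no main assessment exists at the stated time. Two people could then report the same result under different time points. If seven months is instead the programme length, section 3.1 does not say so. It would also be unclear whether the result describes the end of the programme or some weeks or months after it. Wait-list families have no programme period before follow-up, so for them a count from programme start has no meaning.

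The session count looks like a plain contradiction. A review after session 10 cannot happen in a seven-session programme, which would leave no compliance review after session 6.

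**Working it through.** **1. Label against schedule.** Counted from randomization, the gap between label and visit is 8 − 7 = 1 month to 10 − 7 = 3 months. No section counts seven months from randomization. Wherever else the figure appears (Study Summary, 4.1, 19.1, 25.0) it is the length of the programme. On that reading the label names the programme that has just ended, and the four schedule statements give the date of the visit. The two are compatible.

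**2. How long after the programme is the visit?** Let L be the lag in months from randomization to session 1. The text gives no value for L. The timeline grid in 25.0 came through without its shading, so it cannot be said to be absent altogether. I assume 0 to 2 months. The end of the programme can be taken as L + 7 (seven full months) or about L + 6 (the seventh of seven monthly sessions). Visit minus end is (8 to 10) − end:

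| L (assumed) | End = L + 7 | End = L + 6 |
|---|---|---|
| 0 | 1 to 3 months after | 2 to 4 months after |
| 1 | 0 to 2 months after | 1 to 3 months after |
| 2 | 1 month before to 1 month after | 0 to 2 months after |

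The answer moves with two choices that the text does not settle, so no single gap can be held against the plan. The one entry before programme end also sits badly with the name of the visit.

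**3. Does the label enter the analysis or sample size?** Inputs from section 17.2: effect size 0.25, within-child correlation 0.9, 80% power. From 17.1: two-sided 5%. I take the outcome SD as 1.

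- Residual SD after baseline adjustment = √(1 − 0.9²) = √0.19 = 0.436.
- n per group = 2 × (1.960 + 0.842)² × 0.19 / 0.25² = 47.7, so 48 per group and 96 in total, as stated.
- Power at 48 per group (normal approximation) = 0.802.
- Attrition: 120 × 0.85 = 102, which agrees with the plan's figure of about 100.

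No month appears in any of these. The correlation could depend on the interval between measurements: at 48 per group, an assumed 0.85 gives power 0.64 and 0.92 gives 0.88. But the visit takes place on the same date whichever way the label is read, so the label cannot move the correlation.

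**4. Between-arm comparability.** Both arms are measured in the same window, counted from randomization. Wait-list families are offered the programme only after follow-up data collection (section 4.1, Stage 3), so controls have not been offered it at either 7 or 8-10 months.

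**5. Session count.** Of the review points 3, 6 and 10, two are at most 7 and one exceeds it by 10 − 7 = 3. Two of three reviews can occur, the later after 6/7 = 86% of sessions. Adding the four support calls gives 7 + 4 = 11, so that does not explain the ten. Section 2.2 reports ten monthly sessions in the earlier urban trial. Carry-over from it is plausible but not proven. Attendance is logged at each session for the travel gift card (section 12.5). Injury data and adverse event review in 19.1 run on their own timetables and do not depend on the session count.

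**The case for a change.** The strongest case for a change is that section 3.1 ought to define the time point by itself, that the inconsistent wording appears three times, and that the repair costs only a sentence. The programme-length reading also leaves section 3.1 without an origin that applies to controls. In addition, section 4.1 adds two extra child height and weight measurements without dates, one of which might be mistaken for a seven-month assessment.

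What stands is that the label is loose and a cross-reference would be tidier. The rest is answered elsewhere in the protocol. The origin common to both arms is randomization, and four sections state it consistently. The extra measurements are called midpoint or interim, never post-intervention, so they do not compete with the primary visit. Section 17.1 says which claim is intended: the immediate effect, as distinct from the sustained one. Any visit window leaves some gap after the programme ends, and the same gap applies in both arms.

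On session 10 the contradiction is real: the listed review cannot take place. The documents do not say that it was meant as an end-of-programme review. A review after the last session could not alter delivery to the families just treated. If the sponsor wanted one after Cohort 1 to inform Cohort 2, the attendance log would supply it.

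**Conclusion.** No change to the plan follows. The timing point is an unclear parenthesis: seven months most naturally means programme length, and the visit itself is fixed consistently at 8-10 months after randomization for both arms. An analyst would use the post-intervention visit and report its window. The 1 to 3 month discrepancy arises only if the label is counted from randomization, a reading no other section supports. The effect on sample size, bias and analysis is nil; 48 per group reproduces without reference to the label.

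The session-10 entry is a clerical slip that removes one of three compliance reviews. It affects process monitoring only, and the attendance data exist regardless. Both could be tidied if the protocol were amended for another reason, with the sponsor reconciling the review points with the session count.

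This rests on two assumptions: that the four matching schedule statements describe what is done, and that seven months in section 3.1 carries the meaning it has elsewhere in the document.
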